#### 4.2. Exclusion Criteria

Patients are to be excluded from the study if they meet any of the following criteria:

4.2.1. AML is of the sub-type of acute promyelocytic leukemia.

For Part 1 of the study, having received more than one induction systemic therapy for AML or having received a standard dose or high dose ara-C containing regimen for MDS; for Part 2 of the study, having received any systemic therapy for AML or having received hypomethylating agents or cytotoxic chemotherapy for the preceding MDS or myeloproliferative diseases (MPD); for Part 3 and 4 of the study, having received a standard dose or high dose ara-C containing regimen for the preceding MDS.

- 4.2.2. Patients with known central nervous system (CNS) involvement by leukemia should be excluded from this clinical trial because of their poor prognosis and because they often develop progressive neurologic dysfunction that would confound the evaluation of neurologic and other adverse events.
- 4.2.3. Uncontrolled intercurrent illness including, but not limited to ongoing or active infection, active cancer(s) other than AML or MDS, symptomatic congestive heart failure, unstable angina pectoris, cardiac arrhythmia, or psychiatric illness/social situations that would limit compliance with study requirements. Patients receiving intravenous antibiotics for infections that are under control may be included in this study. Active cancer other than AML or MDS refers to cancer that requires systemic chemotherapy or biological therapy within 6 months of the study entry. Patients who have received only hormonal therapy in the neoadjuvant or adjuvant setting in the past 6 months may participate in this study.
- 4.2.4. Pregnant or lactating women
- 4.2.5. Known to be HIV-positive

### 4.3. Removal of Patients from Therapy

Patients have the right to withdraw from the study at any time for any reason. The investigator has the right to withdraw patients from the study according to his/her discretion. When a patient discontinues treatment early, every effort will be made to conduct a post-treatment follow-up visit within 4 weeks after the last dose of study drug or prior to the initiation of new treatment. This post-treatment evaluation may be conducted over the phone if the patient is unable to return to the clinic. The reason(s) for withdrawal must be recorded.

Criteria for terminating participation in the study are listed below:

- Clinically significant progressive disease defined as > 50% increase in the percentage of blasts in bone marrow or peripheral blood over baseline to reach at least 20% blasts in bone marrow or peripheral blood by two assessments while on treatment with an adequate dose
- Lack of efficacy refers to treating physician's judgment that patients are unlikely to benefit from continuation of treatment despite not meeting the criterion of clinically significant progressive disease.
- Unacceptable toxicity
- Patient withdrawal of consent for treatment
- Investigator's discretion that it is in the best interest of the patient to withdraw
- Intercurrent illness: a condition, injury, or disease unrelated to cancer in the opinion of the investigator, that renders continuing sapacitabine treatment unsafe or regular follow-up impossible

- General or specific changes in the patient's condition that renders the patient ineligible for further treatment
- Noncompliance with study medication or protocol-required evaluations and followup visits
- Termination of the clinical trial by the sponsor

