### 4.1. Eligibility Criteria

Patients must fulfill all of the following criteria:

- 4.1.1. For Part 1 of the study, a histologically or pathologically confirmed diagnosis of AML based on WHO classification which is previously untreated by systemic therapy or is in first relapse after achieving a complete remission (CR or CRp) to initial induction, consolidation and/or maintenance therapy; a histologically or pathologically confirmed diagnosis of MDS based on French-American-British (FAB) classification with an IPSS score of intermediate -2 or high - risk which has been previously treated with hypomethylating agents. For Part 2 of the study, a histologically or pathologically confirmed diagnosis of AML based on WHO classification which is previously untreated by systemic therapy in the setting of significant concomitant medical illnesses defined by having a HCTCI of 2 and higher (See Appendix B). For Part 3 of the study, a histologically or pathologically confirmed diagnosis of AML preceded by MDS based on WHO classification after receiving hypomethylating agents for the preceding MDS but the newly diagnosed AML has not been treated with any systemic anti-leukemic therapy. For Part 4 of the study, a histologically or pathologically confirmed diagnosis of MDS based on FAB classification with an IPSS score of intermediate-2 or high- risk and 6 - < 20% blasts in bone marrow which has been previously treated with hypomethylating agents.
- 4.1.2. Age  $\geq 70$  years for AML or  $\geq 60$  years for MDS

- 4.1.3. Eastern Cooperative Oncology Group (ECOG) performance status 0-2 (See Appendix C)
- 4.1.4. Adequate renal function
  - Creatinine  $\leq 1.5 \times ULN$
- 4.1.5. Adequate liver function
  - Total bilirubin or direct bilirubin ≤ 1.5 x ULN
  - Alanine aminotransferase (ALT or SGPT)  $\leq 2.5$  x institutional upper limit of normal (ULN) or  $\leq 5$  x ULN if the liver is involved by leukemia
- 4.1.6. Life expectancy reasonably adequate for evaluating the treatment effect
- 4.1.7. Patient must be able to swallow capsules.

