	(1) For patients with pretreatment hemoglobin < 11 g/dL, >2g/dL increase in hemoglobin; for RBC transfusion - dependent patients, transfusion - independence*				
	(2) For patients with a pretreatment platelet count <100,000/mm³, an absolute increase of ≥30,000/mm³; for platelet transfusion-dependent patients, stabilization of platelet counts and platelet transfusion independence*.				
	(3) For patients with absolute neutrophil count (ANC) $< 1,500/$ mm  before therapy, $\ge 100\%$ increase, or an absolute increase $> 500/$ mm  , whichever is greater.				
	Minor response:				
	(1) For patients with pretreatment hemoglobin < 11 g/dL, 1-2 g/dl increase in hemoglobin; for RBC transfusion – dependent patients, 50% decrease in transfusion requirements.				
	(2) Platelet response: for patients with a pretreatment platelet count $<100,000/\text{mm}^3, \ge 50\%$ increase in platelet count with a net increase $>10,000/\text{mm}^3$ but $<30,000/\text{mm}^3$ .				
	(3) For patients with absolute neutrophil count (ANC) $< 1,500/$ mm  before therapy, $\ge 100\%$ increase, but absolute increase $< 500/$ mm  .				
Stable disease (SD)**	Failure to achieve at least HI, but no evidence of clinically significant progression for > 16 weeks.				

\*independent of transfusions or transfusion –dependence refer to no packed red blood cell transfusion for 2 weeks and no platelet transfusion for 1 week .

Transfusion requirements for each patient are defined as the number of weeks during which at least one transfusion for red blood cells (RBCs) or platelets is administered and the mean number of units of RBC and platelet transfusions administered per month.

CYCLACEL LTD CONFIDENTIAL 34 of 56

\*\* for Part 2, 3 and 4 of the study only

Clinical benefit is defined as the achievement of CR, CRp, PR, major HI or SD. The duration of clinical benefit is measured from the earliest time when the patient achieved CR, CRp, PR or major HI to the first date when the major HI is lost; if the patient only achieved SD, the duration of clinical benefit is measured from the date of randomization or registration to the first date when clinically significant progression of disease is observed.

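### Stable disease rests on a progression rule that marrow cannot meet from a baseline of about 67% blasts, and that lets some Part 4 patients pass 20% blasts, so worsening disease can be scored as clinical benefit

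*Combined protocol and SAP*

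**What the plan says.** Section 4.3 lists clinically significant progressive disease as a reason to end participation. It has two joint conditions. The first is relative: "Clinically significant progressive disease defined as > 50% increase in the percentage of blasts in bone marrow or peripheral blood over baseline". The second is a floor with confirmation: "to reach at least 20% blasts in bone marrow or peripheral blood by two assessments while on treatment with an adequate dose". A separate reason, lack of efficacy, covers patients whom the physician judges "unlikely to benefit from continuation of treatment despite not meeting the criterion of clinically significant progressive disease".

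Table 6 in Section 9 defines SD as "Failure to achieve at least HI, but no evidence of clinically significant progression for > 16 weeks", and a footnote limits it to certain parts: "for Part 2, 3 and 4 of the study only". Table 6 does not refer back to Section 4.3, but no other definition of the term exists. There is no route through an absolute rise, a rise from nadir, or a move out of the MDS range.

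Section 4.1 admits Part 4 patients with "6 - < 20% blasts in bone marrow". It sets no upper blast limit for AML.

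SD is one of the components of clinical benefit, which is:
- the endpoint of the Parts 3/4 futility rule and one of the conditions for adding patients (Section 11.3.1);
- a co-primary endpoint of Part 2 according to Sections 2, 3.1, 11.2 and 11.4 and the definition below Table 6. The opening paragraph of Section 9 leaves SD out of the Part 2 endpoint.

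**The concern.** SD should mean that the disease has held. Under a purely relative rule, a patient with a high baseline has no room left in the marrow to progress. A Part 4 patient near the top of the eligible range can leave that range and still count as stable.

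Nor does the protocol ensure that such patients leave treatment before 16 weeks. The last row of Table 4 continues study drug where blasts have increased from baseline. Removal for lack of efficacy is, by its own wording, not progression, and Table 6 does not say whether it bars SD.

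The stated purpose of the Parts 3/4 screen is to reject insufficiently active schedules. If worsening disease is scored as benefit, the screen loses some of its ability to do so.

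**Working it through.** **1. Level needed to progress.** Both conditions must hold, so follow-up blasts must exceed 1.5 × baseline and be at least 20%.

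**2. High AML baselines (Parts 2 and 3).** Blasts cannot exceed 100%, and 100 / 1.5 = 66.7%.
- Baseline 66%: needs more than 99%, which is possible.
- Baseline 67%: needs more than 100.5%, which is impossible.
- Baseline 70%: needs more than 105%, so a marrow rise from 70% to 95% is not progression.

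Reading the 50% as percentage points does not help: from a baseline of 50%, more than 100% would be needed. The limit applies to each compartment separately, so blood can still show progression unless blood blasts also start at about 67% or more.

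**3. Part 4.** The relative condition becomes the binding one above 20 / 1.5 = 13.3%.

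| Baseline marrow blasts | Level that counts as progression |
|---|---|
| 6% to 13.3% | 20% |
| 15% | more than 22.5% |
| 18% | more than 27% |
| 19% | more than 28.5% |

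A rise from 18% to 26% gives 26 / 18 = 1.44, a 44% increase, so the marrow criterion is not met although the 20% limit has been passed. The affected band, 13.3% to below 20%, is (20 − 13.3) / (20 − 6) = 48% of the eligible range by width. The documents give no baseline distribution, so this is not a share of patients.

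**4. The plan's own figures.** The Parts 3/4 rule stops an arm at 0/10 or at most 1/17. With true benefit rate p, P(stop) = (1 − p)^10 + 10p(1 − p)^16.
- p = 0.05: 0.599 + 0.220 = 0.819 (Table 9: 0.822)
- p = 0.10: 0.349 + 0.185 = 0.534 (Table 9: 0.54)
- p = 0.15: 0.197 + 0.111 = 0.308 (Table 9: 0.313)

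Table 9 is reproduced. For Part 2, the chance of at least 1/12 and then at least 4/24 is 0.029 at a 5% rate and 0.951 at 30%, in line with the stated 5% error rates.

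**5. Illustration.** Take a true benefit rate of 5%, the Part 2 inactivity cut-off, and add SD scored only through these gaps. The added share is an assumption.

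| Added SD | Observed rate | Parts 3/4: arm stopped | Part 2: at least 4/24 | Part 2: also at least 11/36 |
|---|---|---|---|---|
| 0 points | 5% | 82% | 2.9% | below 0.01% |
| 5 points | 10% | 53% | 21% | 0.06% |
| 10 points | 15% | 31% | 48% | 1.4% |

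The last column applies the final Part 2 clinical benefit criterion in Section 11.2, at least 30% of 36 patients (0.30 × 36 = 10.8, so 11), after both earlier stages are passed.

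**The case against.** The case on the other side is substantial.

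- **Blood is a second route.** A patient with 80% marrow blasts and few in blood still progresses once blood blasts rise by more than half and reach 20%. This stands, and it narrows the high-baseline gap.
- **SD needs more than 16 weeks.** Many patients whose disease worsens will die or leave earlier, and a patient removed at week 6 for lack of efficacy does not thereby gain 16 weeks of stability. This stands as a limit on frequency. It does not close the gap, because Table 4 continues drug when blasts rise and Table 6 is silent on early removal.
- **A demanding definition may be deliberate.** Section 9 asks for a second assessment to avoid acting on a temporary flare. That justifies confirmation, but not a threshold above 100%.
- **The added 5 or 10 points have no source.** The AML and MDS gaps differ, and the 5% cut-off may already include SD scored this way, in which case adding to it would count some patients twice. This stands; the figures are illustrative only.
- **The decisions are partly protected.** In Parts 3 and 4 the primary endpoint and the selection criterion are 1-year survival. Adding patients is optional, also requires a 30-day death rate of 20% or less, and under Section 11.4 those patients are analysed separately.

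A reader might infer from the 4/24 figures that Part 2 has a 21% or 48% false-positive rate. Section 11.2 does declare sufficient activity at that step, but it then enrols to 36 and requires a 30% benefit rate or a 20% CR/CRp rate. The first is rarely met in the illustration, and the second does not use SD.

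**Conclusion.** The gap in the definition is real and follows from the text alone. The marrow criterion cannot be met from a baseline of about 67% blasts. Part 4 patients starting between 13.3% and below 20% can pass the protocol's MDS limit without progressing. Worsening disease can therefore be scored as SD and so as clinical benefit.

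This should be fixed because clinical benefit drives the Parts 3/4 futility and expansion rules and, where SD is included, a Part 2 co-primary endpoint. The size is uncertain: the fall in stopping probability from 82% to 53% or 31% rests on the assumed 5 or 10 points.

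Three stronger readings are not supported:
- That worsening disease is routinely counted as benefit. The blood route and the 16-week requirement make *can be* the most the text allows.
- That the screen is shown to pass inactive schedules. No document figure gives the share affected, and 1-year survival, on which schedules are selected, does not depend on SD.
- That every large rise in Part 4 is a fault in the rule. A patient going from 6% to 19% has tripled but has not crossed the protocol's own limit, and the fix below leaves that case as it is.

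Part 1 is unaffected because SD is not used there.

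**What to change.** Leave the treatment-removal rule in Section 4.3 unchanged and add an endpoint-scoring rule for SD to Table 6:

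1. SD requires that the patient was still on study past 16 weeks, had not been removed for lack of efficacy by then, and had started no other anti-leukemic therapy.
2. In Part 4, marrow or blood blasts of 20% or more on two assessments are not SD, whatever the relative rise.
3. For AML baselines from which a rise of more than 50% in marrow is impossible, the sponsor should pre-specify an attainable scoring criterion from blast values already collected. It should not switch abruptly at a baseline such as 66%. For example, a no-rise rule above that level would deny SD to a patient moving from 67% to 68%, while one moving from 60% to 89% (a 48% rise) kept it.
4. The rule that ends the duration of clinical benefit in SD-only patients, below Table 6, should use the same scoring, so that SD status and SD duration agree.
5. Reconcile the opening paragraph of Section 9, which omits SD from the Part 2 endpoint, with the sections that include it.

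The cost is wording in Table 6 and the text around it. Blast counts and withdrawal reasons are already recorded. The clinical benefit rate will be somewhat lower. After the first post-treatment marrow, Table 5 asks for marrows only as clinically indicated, so scoring will often rest on blood blasts.

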#### 5. REGISTRATION AND RANDOMIZATION PROCEDURES

The patient registration and randomization procedures will be described in the Operations Manual.

#### 6. TREATMENT PLAN

#### 6.1. Treatment Administration

For Part 1 of the study, AML patients will be stratified by previously untreated vs. treated for AML. There are no stratification factors for MDS patients. All patients will be randomized 1:1:1 to receive one of the following dosing schedules:

7-day low dose (Arm A): 200 mg b.i.d. x 7 consecutive days (Day 1-7) every 4 weeks

7-day high dose (Arm B): 300 mg b.i.d. x 7 consecutive days (Day 1-7) every 4 weeks

3-day high dose (Arm C): 400 mg b.i.d. x 3 consecutive days per week for 2 weeks (Day 1-3, 8-10) every 4 weeks

For Part 2 of the study: AML patients will receive sapacitabine at 300 mg b.i.d. x 3 consecutive days per week for 2 weeks every 4 weeks

For Part 3 of the study: AML patients will be stratified by prior treatment with decitabine for the preceding MDS (Yes or No) and randomized 1:1:1 to receive one of the following 3 dosing schedules:

Arm D: 200 mg b.i.d. x 7 consecutive days every 4 weeks

Arm E: 300 mg q.d. x 7 consecutive days every 4 weeks

Arm F: 300 mg b.i.d. x 3 consecutive days per week for 2 weeks every 4 weeks

For Part 4 of the study: MDS patients will be stratified by prior treatment with decitabine for MDS (Yes or No) and randomized 1:1:1 to receive one of the following 3 dosing schedules

Arm G: 200 mg b.i.d. x 7 consecutive days every 4 weeks

Arm H:  $300 \text{ mg } q.d. \times 7$  consecutive days every 4 weeks

Arm I: 100 mg q.d. x 5 consecutive days per week for 2 weeks every 4 weeks

Treatment will begin within 7 days of randomization or registration and be administered orally on an outpatient basis unless the patient is hospitalized for reasons other than drug-related toxicities. Patients who are assigned to *b.i.d.* dosing will receive two doses of sapacitabine per day, approximately 12 hours apart. Sapacitabine should be taken within one hour prior to a meal, if possible. Patients who are assigned to *q.d.* dosing will receive one dose of sapacitabine per day which should be taken within one hour prior to breakfast if possible. Patient compliance with study medication will be monitored by capsule count. There will be no make-up dosing for a dose that is missed due to forgetfulness or vomiting. One treatment cycle is 4 weeks. The timing of the subsequent cycles of treatment may vary depending on the disease status, and toxicities.

### 6.1.1. Intra-patient Dose Escalation

In Part 1 of the study, for patients who were assigned to the 7-day low dose arm (Arm A), have tolerated treatment well and have not achieved a CR, the dose may be increased up to 300 mg b.i.d. x 7 days every 4 weeks or up to 400 mg b.i.d. x 3 consecutive days per week for 2 weeks every 4 weeks at the investigator's discretion. In Part 2 of the study, for patients who have tolerated treatment well and have not achieved a CR, the dose may be increased to up to 400 mg b.i.d. x 3 consecutive days per week for 2 weeks every 4 weeks at the investigator's discretion. In Part 3 of the study, the dose may be increased up to 300 mg b.i.d. x 7 days every 4 weeks for patients who were randomized to 200 mg b.i.d. x 7 days every 4 weeks and up to 400 mg b.i.d. x 3 consecutive days per week for 2 weeks every 4 weeks for those who were randomized to 300 mg b.i.d. x 3 days/week for 2 weeks every 4 weeks according to Table 4; there will be no dose escalation for patients who were randomized to 300 mg q.d. x 7 days every 4 weeks because safety experience at higher doses is limited. In Part 4 of the study, the dose may be increased up to 300 mg b.i.d. x 7 days every 4 weeks for patients who were randomized to 200 mg b.i.d. x 7 days every 4 weeks; there will be no dose escalation for patients who were randomized to 300 mg  $q.d. \times 7$  days every 4 weeks; dose escalation up to 150 mg q.d. x 5 days/week for 2 weeks may be allowed for patients who were randomized to 100 mg q.d. x 5 days/week for 2 weeks every 4 weeks after discussion with the study chair and medical monitor.

### 6.2. Dose Reduction Scheme and Treatment Delay

For treatment on Day 8 of Cycle 1 and on Day 1 and 8 of all subsequent cycles, dosing will not start until clinically significant and drug-related non-hematologic toxicities have resolved to ≤ grade 1 or baseline. After recovery, a dose reduction will be instituted for grade 3-4 drug-related non-hematologic toxicities for the next treatment cycle or next week of dosing according to Table 3:

Table 3 Treatment Delay and Dose Modification for ≥ grade 3 Drug-related Non-Hematologic Toxicities

Treatment Arm	Starting Dose	1 st Dose Reduction	2 nd Dose Reduction
Part 1 of the study			
7-day low dose (Arm A)	200 mg b.i.d. x 7 consecutive days every 4 weeks	150 mg b.i.d. x 7 consecutive days every 4 weeks	100 mg b.i.d. x 7 consecutive days every 4 weeks
7-day high dose (Arm B)	300 mg b.i.d. x 7 consecutive days every 4 weeks	250 mg b.i.d. x 7 consecutive days every 4 weeks	200 mg b.i.d. x 7 consecutive days every 4 weeks
3-day high dose (Arm C)	400 mg b.i.d. x 3 consecutive days per week for 2 weeks every 4 weeks	350 mg b.i.d. x 3 consecutive days per week for 2 weeks every 4 weeks	300 mg b.i.d. x 3 consecutive days per week for 2 weeks every 4 weeks
Part 2 of the study			
	300 mg b.i.d. x 3 consecutive days per week for 2 weeks ever y 4 weeks	250 mg b.i.d. x 3 consecutive days per week for 2 weeks every 4 weeks	200 mg b.i.d. x 3 consecutive days per week for 2 weeks every 4 weeks
Part 3 of the study			
Arm D	200 mg b.i.d. x 7 consecutive days every 4 weeks	150 mg b.i.d. x 7 consecutive days every 4 weeks	100 mg b.i.d. x 7 consecutive days every 4 weeks
Arm E	300 mg q.d. x 7 consecutive days every 4 weeks	250 mg q.d. x 7 consecutive days every 4 weeks	200 mg q.d. x 7 consecutive days every 4 weeks
Arm F	300 mg b.i.d. x 3 consecutive days per week for 2 weeks ever y 4 weeks	250 mg b.i.d. x 3 consecutive days per week for 2 weeks ever y 4 weeks	200 mg b.i.d. x 3 consecutive days per week for 2 weeks ever y 4 weeks
Part 4 of the study			
Arm G	200 mg b.i.d. x 7 consecutive days every 4 weeks	150 mg b.i.d. x 7 consecutive days every 4 weeks	100 mg b.i.d. x 7 consecutive days every 4 weeks
Arm H	300 mg q.d. x 7 consecutive days every 4 weeks	250 mg q.d. x 7 consecutive days every 4 weeks	200 mg q.d. x 7 consecutive days every 4 weeks
Arm I	100 mg q.d. x 5 consecutive days per week for 2 weeks every 4 weeks	50 mg q.d. x 5 consecutive days per week for 2 weeks every 4 weeks	50 mg q.d. x 5 consecutive days every 4 weeks

Patients who had treatment delay > 2 weeks due to drug-related non-hematologic toxicities will also have dose reductions according to Table 3.

Dose reduction for drug-related toxicities may be undertaken temporarily or permanently for individual patients to ensure safety according to the assessment and judgment of the investigator in the following situations:

- Decrease dose by 50 mg b.i.d. (Arm A, B, C, D, F, G and Part 2) or 50 mg q.d.(Arm E, H, I) for grade 2 toxicity in a frail patient (See Appendix D)
- Decrease dose by 100 mg b.i.d. (Arm A, B, C, D, F, G and Part 2), or 100 mg q.d. (Arm E, H) or 50 mg q.d. (Arm I) for  $\geq$  grade 3 toxicity in a frail patient or a patient who has experienced more than one  $\geq$  grade 3 drug-related toxicity.

Decisions on treatment delay and dose modifications for drug-related hematologic toxicities should be guided by findings from bone marrow biopsy and/or aspirate as well as time to absolute neutrophil count (ANC) and platelet count recovery according to Table 4. Deviations from the guidelines are permitted to ensure safety and serve the best interest of the patient according to the assessment and judgment of the investigator. The reason for deviating from the guidelines should be documented in source documents.

Table 4 Guidelines on Treatment Delay and Dose Reduction for Hematologic Toxicities

Finding from bone marrow biopsy/aspirate	ANC ≥1000 and platelet count ≥100,000 by or on Day 28 of the cycle	ANC < 1000 or platelet count <100,000 on or after Day 28 of the cycle
Blasts are less than or equal to 5%	Administer study drug;  Decrease dose by 50 mg b.i.d* or 50 mg q.d.** for clinically significant and drug-related hematologic toxicity during the previous cycle	Hold study drug and repeat bone marrow when ANC and platelet count recover to baseline or better; if bone marrow blasts remains at 5% or less, continue to hold the study drug until ANC $\geq$ 1000 and platelets $\geq$ 100, 000 or until bone marrow blasts are increasing to $>$ 5%, whichever comes first; decrease by 100 mg $b$ , $i$ . $d$ * or 100 mg $q$ . $d$ .** for delay in ANC and platelet count recovery to the best level on study beyond Day 42
Blasts are >5% but ≤ 10%	Administer study drug; decrease dose by 50 mg b.i.d.* or 50 mg q.d.** for clinically significant and drug-related hematologic toxicity during the previous cycle	For AML patients, hold study drug and repeat bone marrow in 1-2 weeks; if bone marrow blasts are decreasing, continue to hold the study drug until ANC ≥ 1000 and platelets ≥100, 000 or the recurrence of bone marrow blasts to >10%, whichever comes first; if bone marrow blasts are stable or increasing, administer the study drug; for MDS patients, hold study drug until ANC and platelet count have recovered to the best level on study or the recurrence of bone marrow blasts to >10%, whichever comes first.
		decrease sapacitabine dose by 50 mg $b.i.d*$ or 50 mg $q.d.**$ for delay in ANC and platelet count recovery to the best level on study beyond Day 42.
Blasts have decreased 25% or more from baseline but are still >10 %	Administer study drug; decrease dose by 50 mg b.i.d.* or 50 mg q.d.** for clinically significant and drug-related hematologic toxicity during the previous cycle	If ANC and platelet count have not recovered to baseline or better, hold study drug until ANC and platelet count recover to baseline or better or Day 42, whichever comes first; decrease dose by 50 mg b.i.d.* 50 mg q.d.** for clinically significant and drug-related hematologic toxicity during the previous cycle or for delay in ANC and platelet count recovery to best level on study beyond Day 42 due to drug-related hematologic toxicity
Blasts have decreased less than 25% from baseline, have increased from baseline or have increased from the best response in bone marrow	Administer study drug****	Administer study drug****

\* for patients enrolled on Arm A, B, C, D, F, G and Part 2.

\*\* For patients enrolled on Arm E, H, I.

\*\*\* For patients in Part 1 of the study who were assigned to the 7-day low dose arm (Arm A) and have tolerated treatment well, consider intra-patient dose escalation up to 300 mg b.i.d. x 7 days every 4 weeks or up to 400 mg b.i.d. x 3 consecutive days per week for 2 weeks every 4 weeks; for patients assigned to the 7-day high dose (Arm B) and 3-day high dose (Arm C) and have had dose reductions for hematologic toxicities, consider dose escalation back up to the originally assigned dose. For patients in Part 2 of the study who have tolerated the treatment well, consider intra-patient dose escalation up to 400 mg b.i.d. x 3 consecutive days per week for 2 weeks every 4 weeks. In Part 3 of the study, the dose may be increased up to 300 mg b.i.d. x 7 days every 4 weeks for patients who were randomized to 200 mg b.i.d. x 3 days/week for 2 weeks every 4 weeks; there will be no dose escalation for patients who were randomized to 300 mg q.d. x 7 days every 4 weeks. In Part 4 of the study, the dose may be increased up to 300 mg b.i.d. x 7 days every 4 weeks for patients who were randomized to 300 mg q.d. x 7 days every 4 weeks. In Part 4 of the study, the dose may be increased up to 300 mg b.i.d. x 7 days every 4 weeks for patients who were randomized to 300 mg q.d. x 7 days every 4 weeks. In Part 4 of the study, the dose may be increased up to 300 mg b.i.d. x 7 days every 4 weeks for patients who were randomized to 300 mg q.d. x 7 days every 4 weeks; dose escalation up to 150 mg q.d. x 5 days/week for 2 weeks may be allowed for patients who were randomized to 100 mg q.d. x 5 days/week for 2 weeks every 4 weeks after discussion with the study chair and medical monitor.

Dosing will be withheld in the presence of non-drug related grade 3 or grade 4 adverse events (AEs) if the investigator feels that it is unsafe to continue the administration of sapacitabine.

In general, a patient who requires more than two dose reductions, will be removed from the study unless, in the opinion of the investigator, the patient is experiencing a clinical benefit defined as achieving CR, CRi, or stable disease (SD) without unacceptable toxicities. In such instances, a decision regarding the continuation of treatment and further dose reductions will be made on an individual basis in consultation with the medical monitor and the justification will be recorded in the source documents.

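### Row 4 of Table 4 overlaps rows 1, 2 and 3 with no stated precedence, so a patient with low counts can meet both a hold and an administer instruction

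*Combined protocol and SAP*

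**What the plan says.** Section 6.2 of the protocol sends decisions on drug-related hematologic toxicity to Table 4, which crosses four marrow findings with two count columns. The low-count column is headed "ANC < 1000 or platelet count <100,000 on or after Day 28 of the cycle".

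- Row 1 covers blasts up to 5%. With low counts the drug is held, and "if bone marrow blasts remains at 5% or less, continue to hold the study drug until ANC" and platelets reach their thresholds or blasts rise above 5%.
- Row 2 covers blasts above 5% and up to 10%. For AML the drug is held and the marrow repeated in 1 to 2 weeks. The other instruction reads "for MDS patients, hold study drug until ANC and platelet count have recovered to the best level on study" or until blasts recur above 10%.
- Row 3 covers a fall of at least 25% from baseline with blasts still above 10%. The drug is held if counts have not returned to baseline, until they do or until Day 42.
- Row 4 is worded "Blasts have decreased less than 25% from baseline, have increased from baseline or have increased from the best response in bone marrow". Both count columns say to give the drug, with a marker of four asterisks.

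The only footnote that fits that marker is printed with three asterisks and deals with dose escalation. For Arm A it covers patients who "have tolerated treatment well, consider intra-patient dose escalation up to 300 mg b.i.d. x 7 days every 4 weeks" or move to a 3-day alternative. Section 6.2 also leaves discretion to the investigator, with the reason documented: "Deviations from the guidelines are permitted to ensure safety and serve the best interest of the patient according to the assessment and judgment of the" (sentence cut short here). Part 4 eligibility (Section 4.1) requires "6 - < 20% blasts in bone marrow which has been previously treated with hypomethylating agents".

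**The concern.** Rows 1 and 2 look at where the marrow is now; row 4 looks only at how it has moved. A marrow can satisfy both, and Section 6.2 does not say which row then governs. In a patient whose counts have not recovered, the two rows give contrary instructions.

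The study drug is myelosuppressive, and Section 3.3 reports that all patients with a CR on the 400 mg 3-day schedule had their dose reduced for myelosuppression. Table 4 applies to every arm, at approximately 25 sites. If sites resolve the overlap differently, the delivered dose of a schedule depends partly on how the table is read. Sections 11.1.2 and 11.3.2 then choose between schedules on observed 1-year survival with 20 patients per schedule, assuming similar toxicity profiles.

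**Working it through.** No sample size or error rate is involved. The check is whether one set of marrow values can meet two rows. The 25% is read as a relative fall from baseline (an assumption; the table does not define it).

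**Row conditions.** Write b for baseline, m for the best on-study value and c for the current value.

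| Row | Condition | Low-count instruction | Release from hold |
|---|---|---|---|
| 1 | c ≤ 5 | Hold | ANC ≥ 1000 and platelets ≥ 100,000, or blasts rising above 5% |
| 2, AML | 5 < c ≤ 10 | Hold, repeat marrow | Blasts stable or rising on repeat; if falling, count recovery or blasts above 10% |
| 2, MDS | 5 < c ≤ 10 | Hold | Counts at best level on study, or blasts above 10% |
| 3 | c ≤ 0.75b and c > 10 | Hold if counts below baseline | Counts at baseline, or Day 42 |
| 4 | c > 0.75b, or c > m | Give | None needed |

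Every marrow meets at least one row: c ≤ 10 falls in row 1 or 2, and c > 10 falls in row 3 or 4. The fault is therefore overlap, not a gap.

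**Three cases, all with ANC < 1000 or platelets < 100,000 on or after Day 28.**

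- (a) Part 4 MDS, b = 8, c = 7, counts below the best level on study. The fall is (8 − 7)/8 = 12.5%, under 25%, so row 4 says give. Since 5 < 7 ≤ 10, row 2 says hold.
- (b) AML, b = 40, m = 12, c = 18, counts below baseline, before Day 42. The fall is (40 − 18)/40 = 55% and 18 > 10, so row 3 says hold. Since 18 > 12, row 4 says give.
- (c) Best value 2%, now 4%. Since 4 ≤ 5, row 1 says hold. Since 4 > 2, row 4 says give. Nothing further need be assumed.

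**Range in Part 4, baseline clauses only.** Rows 2 and 4 share a value when 0.75b < 10, that is b < 10/0.75 = 13.3. With eligible baselines of 6 to < 20, overlap is possible for 6 ≤ b < 13.3. At b = 8 the shared values are 6 < c ≤ 10. At b = 13 they are only 9.75 < c ≤ 10.

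**Range with the best-response clause.** Any rise from the best value brings in row 4 at any baseline. For b = 19, m = 7, c = 9 the fall is (19 − 9)/19 = 53%, so the baseline clauses are not met. But 9 > 7 meets row 4, and 5 < 9 ≤ 10 meets row 2.

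**Does reading order settle it?** If rows are taken from the top, row 4 is left with c > 10 and a fall under 25% (or a rise from baseline). The best-response clause then does nothing, because a patient above 10% and at least 25% below baseline is already in row 3. If row 4 is taken first, it overrides row 1's hold, which continues through rises up to 5%, and row 2's MDS hold, which continues through rises up to 10%. Either order cancels part of the printed text.

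**The case against.** The strongest defence is that Table 4 is offered as guidance. Deviations are permitted, Section 6.1 lets the timing of later cycles vary, and after the marrow before cycle 2 further marrows are done as clinically indicated (Section 7, note h). So the table need not come into play every cycle. This stands and lessens the consequence. It does not settle the conflict: a deviation presupposes one defined instruction. Here a site that holds and a site that doses can both claim compliance, with no reason to document.

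A second defence is that rows 1 and 2 carry their own release rules, which would have little purpose if row 4 captured every rise below those limits. That is a fair reading of intent for those two rows. But it is not stated, and it leaves the best-response clause without effect.

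A third is that low counts alone do not create the conflict in every row. This stands. In row 2 an MDS patient already at the best level on study is not held, and in row 3 a patient with counts back at baseline, or past Day 42, is not held. For AML in row 2 the conflict eases after the repeat marrow if blasts are stable or rising.

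A reader might go further and infer that cytopenic patients in row 4 are in general to be escalated. The documents do not support that. The link rests on matching a four-asterisk marker to a three-asterisk footnote. The option is conditional: tolerance is required in Arm A and Part 2, Arms B and C may only return to the assigned dose, and Arm I needs prior discussion with the study chair and medical monitor. Section 6.1.1 excludes escalation for 300 mg q.d. x 7 days.

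**Conclusion.** The concern holds as a contradiction within Table 4: row 4 overlaps each of the other rows, and with low counts the overlapping rows can direct both a hold and administration. Case (c) shows this on low counts alone; cases (a) and (b) need the count conditions stated with them. For MDS patients in row 2 the conflict persists while blasts stay at or below 10% and counts stay below the best level on study.

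The number of patients affected is unknown. A reader might turn the 6% to 13.3% range into about half of Part 4, since (13.3 − 6)/(20 − 6) = 0.52. That is a share of the eligible baseline range under an assumed even spread. It says nothing about how often counts are low or marrows fall in the shared band, and it leaves out the best-response clause. A reader might likewise infer that schedule selection is biased. The documents allow no estimate of that; what is shown is a route by which delivered dose could differ between sites.

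Correction is warranted because the ambiguity concerns dosing in cytopenic patients and is cheap to remove. No view is taken on which instruction is clinically right.

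**What to change.** By amendment to Section 6.2:

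- make the four rows of Table 4 mutually exclusive, or state which row takes precedence when two apply;
- state whether the count columns are meant to matter in row 4;
- correct the footnote marker so that row 4 points to an existing footnote;
- align the footnote with Section 6.1.1, arm by arm. The footnote's Part 3 and Part 4 sentences repeat phrases in a way that may be reproduction damage, so nothing here rests on them, but they should be checked.

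The sponsor must reconcile the hold and administer instructions; no clinical rule is proposed here. The cost is one table edit and a memo to sites, with no new procedures or patients.
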